### 3.2 Patients randomization and identification

The study participants are randomized using a simple envelopes method. An independent person will generate a random table for 114 records in which 57 will be marked as “M” and 57 will be marked as “B”. According this computer based randomization table cards with letter “B” or “M” will be sealed in 114 numbered envelopes. The randomization table will also be sealed in a separated envelope. The numbered envelopes will be sent to Principal Investigator. The envelope with randomization table will be stored in the Sponsor file.

Each patient is assigned with a special identification code that is only used in the program. The code is assigned to a patient after enrollment and includes the health care facility code and the patient number.

According to the protocol, decoding keys for the identification codes are not provided. Persons authorized by the Sponsor, health care or other regulatory authorities may inspect any program data available to the investigator.

### 3.3 Study duration

The total duration of the study is 48-50 weeks.

Patients' enrollment – 12 months. After screening period (1-14 days) and washout period (7-10 days), every patient will be treated for up to 48 weeks.

### 3.4 Schedule of the study procedures

Prior to the study enrollment, examination to assess conformity with the inclusion/exclusion criteria, to obtain baseline data and ensure washout period (if necessary) will be carried out for a patient. After enrollment and initiation of the investigated treatment, the study procedures will be conducted to assess product tolerability, safety, efficacy and patient compliance. All scheduled visits are mandatory. Washout period will be carried out only for patients with prior antihypertensive therapy. Each patient is to sign the informed consent prior to any study activities including screening / “examination to assess conformity with the in- and exclusion criteria.

Schedule of the study procedures is presented in Table 2.

	Visit 0 Screening	Visit 1	Visit 2	Visit 3	Visit 4
	Day-14...-1	Day 0	Week 8	Week 24	Week 48
Drug administration		+	+	+	+
Dose titration / treatment adjustment		+	+	+	
BP / HBR / Patients' diary analysis	+	+	+	+	+
ECG, K, Na	+			+	
Creatinine	+			+	
ALT/AST	+			+	
Parathyroid hormone	+				
X-ray densitometry, BMD	+				+
Total calcium, Phosphorus	+			+	+
PWV		+			+
IMT + evaluation of subclinical atherosclerosis		+			+
Telomerase activity		+			+
Osteocalcin		+		+	+
Collagen type 1 C-telopeptide		+		+	+
Osteoprotegerin, RANKL		+			+
Safety Information	+	+	+	+	+

### 3.5 Number of patients:

114 patients will be enrolled to the study to ensure the final sample size. The patients will be randomized to one of two treatment groups (moxonidine group or bisoprolol group) using simple

randomization envelopes. It is anticipated that a screening of 300 subjects will be needed in order to enroll the minimum of 100 patients to the study.

According to the study protocol, patients randomization to the control and investigated groups will be carried out randomly and, therefore, it is assumed that the control and the investigated groups will be matched by the basic measured parameters; the number of subjects in the main and control groups is planned to be equal.

The study endpoints are measured prior to the studied product initiation (V1) and after completion of 48-week treatment with the investigated product (V4).

### **3.6 Study procedures**

#### **3.6.1 Screening and washout periods (V0)**

Any patient screening procedures are conducted only after the informed consent to participate in the study is signed. After the informed consent is signed, the patient is assigned with a screening number and **the following procedures** are performed.

The investigator collects patient demographic data (gender, age), significant life history, detailed medical history (duration of hypertension, current antihypertensive drugs and duration of their use), and assesses hypertension severity and grade according to the ESH/ESC recommendations that are listed in Appendix 1. The investigator asks questions about the patient's history of cardiovascular disorders and other significant comorbidities and their treatment.

The researcher gathers information about medications that patient's used during 30 days prior to the screening, asks about intolerance to antihypertensive drugs, especially I1-imidazoline receptors, beta-blockers and ACE inhibitors.

After the conversation with the patient, the investigator conducts a physical examination of organs and organ systems that must include measurement of heart rate, systolic and diastolic blood pressure according to ESH/ESC recommendations that are listed in Appendix 1 [17]. BP is first measured on the right and left arms. Thereafter, during the remaining study period, blood pressure should be measured at the arm with the highest blood pressure on screening. Resting heart rate (bpm) is measured by the standard method used in the physician routine practice. It is recommended to count heart rate for 60 seconds in a sitting position after 5 minutes of rest three times with 2-3 minutes interval between the measurements.

Blood pressure and heart rate are measured in a sitting position after 5 minutes of rest. **Three** measurements are carried out, the average value of the measurements is recorded.

The patient will have the resting standard 12-lead ECG registered. The investigator will record all clinically significant ECG abnormalities.

If the data obtained meet the screening criteria, biochemical (potassium, sodium, creatinine, total calcium, inorganic phosphorus, ALT, AST) and hormone (PTH) fasting blood tests will be conducted for the patient.

Results of the tests (CBC, BMP, pregnancy test) should be obtained prior to the washout period initiation and patient enrollment to verify compliance with screening criteria.

Dual energy X-ray absorptiometry to determine BMD and detect osteopenia will be performed.

After screening investigation results are obtained, if the patient meets screening criteria, the investigator:

- Schedules visit V1 for primary patients and patients who were only administered with fast acting antihypertensives to relieve a hypertension episode;
- Starts washout period for patients taking antihypertensive drugs at the time of screening visit, before proceeding to visit V1.

During the washout period, the investigator will ask the patient to refrain from taking her prior antihypertensives and other antihypertensives. The investigator may prescribe the patient with short acting antihypertensives to relieve a hypertension episode (at the investigator discretion: nifedipine, captopril or other acting products for urgent blood pressure lowering).

Also, a modified lifestyle will be advised, e.g., dieting (according to ESH/ESC recommendations that are listed in Appendix 3), cessation of smoking, physical exercises.

**For washout period conditions and requirements please refer to “Treatment of patients”.**

If the patient does not meet the screening criteria, she should not proceed with the following visits and her data and reason for withdrawal from the study are recorded in the screened patients accountability form.

### **3.6.2 Enrollment visit (V1)**

Enrollment visit is conducted no later than 14 days after signing the informed consent form by the patient.

The investigator documents all significant changes in the history of hypertension and concomitant treatment (including fast acting antihypertensives to relieve a hypertension episode that may be administered during the washout period); the investigator identifies and documents adverse events associated with the protocol procedures, if any, starting from the date of the informed consent signing.

The investigator conducts a physical examination of the patient by organs and organ systems that must include measurement of heart rate, systolic and diastolic blood pressure according to ESH/ESC recommendations that are listed in Appendix 1 [17]. Blood pressure and heart rate are measured in a sitting position after 5 minutes of rest on the arm with the highest BP during screening. Three measurements are done; the average value of the measurements is documented. The investigator assesses hypertension severity and grade according to the ESH/ESC recommendations that are listed in Appendix 2.

Applanation tonometry method is used to measure changes in patient's PWV; duplex ultrasonography of extracranial brachiocephalic arteries is employed to evaluate IMT and subclinical atherosclerosis.

Blood is sampled to investigate bone metabolism: osteocalcin, Ctx, OPG, RANKL.

Blood is sampled to determine telomerase activity.

The investigator may enroll the patient in the study and start the investigated treatment only if the patient meets all the screening criteria to start the treatment.

The investigator randomizes patients to one of two treatment groups by means of the simple envelopes method.

### **Treatment regimens**

- **Group 1** patients receive moxonidine with dose titration up to the maximum, then a patient may be switched to the combination therapy, if necessary (step 2 - adding an ACE inhibitor).
- **Group 2** patients receive bisoprolol with dose titration up to the maximum, then a patient may be switched to the combination therapy, if necessary (step 2 - adding an ACE inhibitor).

The investigator will provide a Group 1 patient with moxonidine 0.4 mg in the amount required for 56 days of treatment plus 7 extra days and additionally moxonidine 0.2 mg in an amount required for 42 days of treatment if the dose is titrated up to 0.6 mg/day.

The patient will take the first moxonidine tablet immediately during the visit after all the visit procedures are completed. The patient will be instructed to take 1 tablet of moxonidine 0.4 mg in the morning, daily. The next visit will be scheduled in week 8 after the enrollment visit (in 56 days  $\pm$  5 days after the enrollment visit).

The patient will be asked to bring all the blisters of investigated product (empty, started and not started blisters) to every visit after the study initiation.

The investigator will give the patient blood pressure self-monitoring diary which is to be used by the patient to daily document her BP values and to bring it to every subsequent visit.

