### **3.6.3 Telephone visits (TV1 and TV2)**

Telephone visits are conducted at week 2 and week 4 after the enrollment visit. The investigator will document the disease history since the last visit, including all adverse events and changes in concomitant treatment.

On the 2nd week telephone visit (**TV1**), the investigator evaluates efficacy, safety and tolerability of the investigated treatment. Patients will continue to take moxonidine 0.4 mg/bisoprolol 5 mg until visit V2. If BP control is insufficient, the investigator may increase moxonidine and bisoprolol doses to 0.6 mg and 7.5 mg QD, respectively.

On the 4th week telephone visit (**TV2**), the investigator evaluates efficacy, safety and tolerability of the investigated treatment. Patients will continue to take moxonidine 0.6 mg/bisoprolol 5 mg until visit V2. If BP control is insufficient with moxonidine 0.6 mg/bisoprolol 7.5 mg QD, the investigator adds perindopril 10 mg QD.

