### **3.6.4 Visit 2 (V2)**

Visit 2 is conducted at week 8 after the enrollment visit. The investigator will document the disease history since the last visit, including all adverse events, changes in concomitant treatment, and changes in concomitant medications doses, if any.

The investigator will analyze the effectiveness of the therapy according to the patient's BP self-monitoring diary data.

The investigator measures blood pressure and heart rate in a sitting position after 5 minutes of rest. **Two** measurements are done; the average value of the measurements is documented. BP is measured on the same arm during the entire study.

The investigator analyzes the patient's compliance based on the number of returned tablets.

The investigator evaluates response to the treatment (target BP reaching), documents it in source documents and decides on further treatment of the patient. If target BP has not been reached, the patient's investigated product dose is titrated according to the study design. If the target BP has been reached, the patient continues with the current treatment until the next visit.

The investigator will invite the patient to the next visit (visit V3) scheduled for week 24 after the enrollment visit (168 days  $\pm$  5 days after the enrollment visit); the patient will be asked to return the investigated medication blisters (empty, started and not started blisters). The patient will be instructed to start taking the provided product the next day morning, 1 tablet per day. The patient will be instructed to report any adverse events (if applicable) to the investigator.

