### **3.9 Product packaging and storage**

#### **3.9.1 Packaging.**

Moxonidine is packaged in original factory blisters; every blister contains 14 tablets.

Bisoprolol is packaged in original factory blisters; every blister contains 10 tablets either every blister contains 50 tablets.

At every visit (V1, V2, V3), the investigator will provide a patient with the product blisters for subsequent treatment period till next visit.

**Storage conditions.** Moxonidine and bisoprolol do not require any special storage conditions.

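### The 0.2 mg moxonidine tablets dispensed at V1 carry no reserve, so an adherent patient raised at week 2 and seen late in the V2 window can run 1 to 6 tablets short before the week 8 BP reading

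*Combined protocol and SAP*

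**What the plan says.** Section 3.6.2 (Treatment regimens) sets two supplies for the moxonidine group at V1. The first is "moxonidine 0.4 mg in the amount required for 56 days of treatment plus 7 extra days". The second, for patients whose dose is raised, is "additionally moxonidine 0.2 mg in an amount required for 42 days of treatment if the dose is titrated up to 0.6 mg/day". No extra days are stated for the second supply. The same section fixes V2 as follows: "The next visit will be scheduled in week 8 after the enrollment visit", with a tolerance of 5 days either way, so any day from 51 to 61 is in window.

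The dose can first be raised by telephone. Section 3.6.3 states: "Telephone visits are conducted at week 2 and week 4 after the enrollment visit". For the week 2 call it adds: "If BP control is insufficient, the investigator may increase moxonidine and bisoprolol doses to 0.6 mg and 7.5 mg QD, respectively".

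Section 3.9.1 gives the dispensing occasions: "At every visit (V1, V2, V3), the investigator will provide a patient with the product blisters for subsequent treatment period till next visit". It also says that moxonidine blisters hold 14 tablets. Section 5.6 names the same three visits and says that the amount supplied must be what the patient needs until the next one. At V2, section 3.6.4 says: "The patient will be instructed to start taking the provided product the next day morning". Section 5.1 likewise starts each new supply on the day after the visit, so the dose on the day of V2 comes from the V1 supply.

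**The concern.** The two tablet strengths are needed over the same interval and up to the same visit, but only one has a reserve for a late visit. A patient raised at the week 2 call has no scheduled contact at which tablets are handed over before V2. If she takes every dose and V2 falls late in its window, her 0.2 mg tablets end before the visit while she still holds 0.4 mg tablets.

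At stake is the V2 reading of the proportion of patients below 140/90 mmHg, one time point of the last secondary endpoint in section 3.10. Some titrated patients could be measured after a few days below their assigned dose.

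The compliance rules would not necessarily flag this. A patient who needed 47 tablets and took the 42 supplied is at 42/47 = 89%, above the 80% limit in section 4.5, and she returns none. It would show only if entered as a dosing deviation under section 5.5.

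**Working it through.** **Inputs**
- 0.4 mg supply: 56 + 7 = 63 days (3.6.2).
- 0.2 mg supply: 42 days (3.6.2).
- V2: day 56, allowed range 56 - 5 = 51 to 56 + 5 = 61 (3.6.2).
- First 0.4 mg dose: day 0, at V1 (3.6.2).
- First opportunity to raise the dose: the week 2 call, taken as day 14 because no window is given for calls (3.6.3). The first 0.6 mg dose is then on day 14 or on the following morning, day 15.
- Blister size: 14 tablets (3.9.1).
- Assumed: 0.6 mg is one 0.4 mg plus one 0.2 mg tablet daily, every dose is taken, and the site dispenses exactly the stated number of days.

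**The plan's own figure.** 56 - 14 = 42, so the stated quantity reproduces exactly for a V2 on day 56. It is 42/14 = 3 full blisters, so rounding to whole packs adds nothing. For 0.4 mg, 63/14 = 4.5, which rounds up to 5 blisters (70 tablets).

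**0.4 mg balance at V2.** Doses run from day 0 to the day of V2, so balance = 63 - (V2 day + 1). Day 56: 63 - 57 = +6. Day 61: 63 - 62 = +1. This supply covers the whole window.

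**0.2 mg balance at V2.** Balance = 42 - (V2 day - first 0.6 mg day + 1).

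| First 0.6 mg dose | V2 day 51 | V2 day 56 | V2 day 57 | V2 day 61 |
|---|---|---|---|---|
| Day 14 | +4 | -1 | -2 | -6 |
| Day 15 | +5 | 0 | -1 | -5 |
| Day 19 | +9 | +4 | +3 | -1 |
| Day 20 | +10 | +5 | +4 | 0 |
| Day 29 | +19 | +14 | +13 | +9 |

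For example, a start on day 15 with V2 on day 61 needs 61 - 15 + 1 = 47 tablets, and 42 - 47 = -5. If the dose on the day of V2 is not counted against the V1 supply, each balance rises by one, and the worst cases become -5 (day 14 start) and -4 (day 15 start).

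**How many patients.** The documents give neither a titration rate nor a distribution of visit days. Suppose that V2 dates spread evenly over the 11 window days and that the raised dose starts on day 15, so that days 57 to 61 (5 of 11) give a shortfall. With 57 patients in the arm:
- 20% raised at week 2: 57 x 0.20 x 5/11 = 5.2
- 40%: 57 x 0.40 x 5/11 = 10.4
- 60%: 57 x 0.60 x 5/11 = 15.5

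The range is about 5 to 16 patients. It mixes shortfalls of one tablet with shortfalls of five and assumes full adherence.

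**With the 0.4 mg reserve applied to 0.2 mg.** 42 + 7 = 49. At day 61 the balance is 49 - 47 = +2 (day 15 start) or 49 - 48 = +1 (day 14 start).

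**The case against.** The strongest reply is that section 5.6 already requires enough product to last until the next visit. V2 is booked at V1, so a site that knows the date will be late could hand over more than 42 tablets. This has some force, but it conflicts with the fixed quantity in section 3.6.2 and does not correct it. A site following 3.6.2 to the letter under-supplies, and the two passages should agree.

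The second reply is that the shortfall is conditional, and this stands in full. A reader might infer that all titrated patients run out. They do not. An early V2, a first 0.6 mg dose on day 20 or later, or enough missed doses (5 of 47 in the worst day 15 case) each removes the shortfall.

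Four other stronger readings are tempting, and the documents do not support them:
- **Patients drop back to 0.4 mg.** This is an inference from the strength they would still hold. No section says what a patient does when the 0.2 mg tablets are used up.
- **The shortfall triggers perindopril at V2.** The synopsis and sections 3.1 and 3.8.3.1 place that step at week 8, but sections 3.6.3 and 5.1 place it at the week 4 call. Section 5.1 also continues the regimen at V2 for any patient below 180/120 mmHg. Those passages contradict one another and need reconciling in their own right, so no consequence can be built on one side of them.
- **The effect is one-sided against moxonidine.** No V1 quantity is stated for bisoprolol, so a shortfall there can be neither shown nor excluded.
- **The same defect recurs at V2 and V3.** No quantities are stated for those dispensings, so no shortfall is shown.

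**Conclusion.** The point holds as a minor supply inconsistency. The 42-day quantity does not fit the plan's own V2 window, and the 0.4 mg quantity given alongside it does. A fully adherent patient raised at week 2 is 0 to 1 tablet short on day 56 and 5 to 6 short on day 61, depending on whether 0.6 mg starts on day 15 or day 14. This rests on a call on day 14, one 0.2 mg tablet a day, and exact dispensing of 42 days.

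The arithmetic is firm, but the effect on results is not. The figure of about 5 to 16 of 57 patients depends on assumed titration rates and evenly spread visits. No change in the responder proportion can be estimated from the documents. The exposure is limited to the V2 time point of one secondary endpoint in a study that describes itself as explorative. The primary endpoint, change in CTX at V4, is not directly affected.

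**What to change.** Reconcile the 42-day quantity in section 3.6.2 with the 5-day tolerance around V2 and with the supply rule in section 5.6. The simplest way is to give the 0.2 mg tablets the 7-day reserve that 3.6.2 already gives the 0.4 mg tablets: 42 + 7 = 49 days. Since 49/14 = 3.5, that means four blisters (56 tablets). No dose or titration rule changes.

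The cost is about one extra 14-tablet blister per moxonidine patient supplied with 0.2 mg tablets, one line in the dispensing instruction, and a new dispensed total for the tablet count at V2.

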### **3.6.3 Telephone visits (TV1 and TV2)**

Telephone visits are conducted at week 2 and week 4 after the enrollment visit. The investigator will document the disease history since the last visit, including all adverse events and changes in concomitant treatment.

On the 2nd week telephone visit (**TV1**), the investigator evaluates efficacy, safety and tolerability of the investigated treatment. Patients will continue to take moxonidine 0.4 mg/bisoprolol 5 mg until visit V2. If BP control is insufficient, the investigator may increase moxonidine and bisoprolol doses to 0.6 mg and 7.5 mg QD, respectively.

On the 4th week telephone visit (**TV2**), the investigator evaluates efficacy, safety and tolerability of the investigated treatment. Patients will continue to take moxonidine 0.6 mg/bisoprolol 5 mg until visit V2. If BP control is insufficient with moxonidine 0.6 mg/bisoprolol 7.5 mg QD, the investigator adds perindopril 10 mg QD.

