Group 2 will receive bisoprolol with the dose titrated to a maximum, and then, if necessary, the patient will be shifted to the combination therapy (Step 2 – adding an ACE inhibitor).

After randomization to moxonidine and bisoprolol groups (V1), patients start treatment with 0.4 mg moxonidine QD or 5 mg bisoprolol QD. If the target BP (<140/90 mmHg) is reached in 2 weeks, the patient continues taking the medication at the same dose. If the target BP is not reached in 2 weeks, the moxonidine dose is increased to 0.6 mg QD, the dose of bisoprolol is increased to 7.5 mg QD. If the target BP is not reached in 2 weeks of treatment with the increased doses, an ACE inhibitor (perindopril) at a dose of 10 mg/day is added at the 8th week of the study. In case of intolerance to perindopril, losartan at a dose of 50 mg/day will be administered.

During the study, the patient will have parameters of efficacy, tolerability and safety of the therapy with moxonidine or bisoprolol regularly assessed.

The study design is shown in Figure 1.

Figure 1. The overall study design

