On 2nd week telephone visit, the investigator evaluates efficacy, safety and tolerability of the investigated treatment. Patients will continue taking moxonidine 0.4 mg QD until next visit V2. If BP control is insufficient, the investigator may increase moxonidine dose to 0.6 mg QD.

On 4th week telephone visit, the investigator evaluates efficacy, safety and tolerability of the investigated treatment. Patients will continue taking moxonidine 0.4 mg (0.6 mg) QD until next visit V2. If BP control is insufficient with moxonidine 0.6 mg QD, the investigator adds perindopril 10 mg QD.

**All group 2 patients** are prescribed with bisoprolol 5 mg monotherapy. At the **V1 enrollment visit**, the patient will be given the medication and will take first dose of bisoprolol in the presence of the investigator. Thereafter, patients will take the medication every morning, during the entire study. The medication will be dispensed to a patient at visits V1, V2, V3, and the patient will start taking the drug on her own on the day following the visit. One tablet of the investigated product should be taken daily, in the morning, regardless of meals.

On 2nd week telephone visit, the investigator evaluates efficacy, safety and tolerability of the investigated treatment. Patients will continue to take bisoprolol 5 mg until visit V2. If BP control is insufficient, the investigator will increase bisoprolol dose to 7.5 mg QD.

On 4th week telephone visit, the investigator evaluates efficacy, safety and tolerability of the investigated treatment. Patients will continue to take bisoprolol 5 mg (7.5 mg) until next visit V2. If BP control is insufficient with bisoprolol 7.5 mg QD, the investigator adds perindopril 10 mg QD.

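### Perindopril is to be added at week 4 in some sections and at week 8 in others, so the week-8 blood-pressure responder proportion has no single meaning

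*Combined protocol and SAP*

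**What the plan says.** **When perindopril is added.** Section 3.1, and the same text under Study Design in the synopsis, says that if the raised dose fails, "an ACE inhibitor (perindopril) at a dose of 10 mg/day is added at the 8th week of the study". The Investigated product and Comparative product rows of the synopsis and sections 3.8.1 and 3.8.2 also give week 8, and 3.8.3.1 reserves perindopril for patients not at target by V2. Section 3.6.3 says of the week-4 call (TV2): "If BP control is insufficient with moxonidine 0.6 mg/bisoprolol 7.5 mg QD, the investigator adds perindopril 10 mg QD". Section 5.1 repeats that week-4 step separately for each arm. The losartan text (synopsis, other permitted agents; section 3.8.4) refers to four weeks of failed monotherapy, which fits the week-4 schedule.

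**What happens at V2 and V3.** Sections 3.6.4 and 3.6.5 call for titration under the study design when target BP has not been reached. Section 5.1 keeps the regimen unchanged at both visits for any BP <180/120 mmHg.

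**The week-2 step.** Section 3.1 is directive for both arms when target is missed: "the moxonidine dose is increased to 0.6 mg QD, the dose of bisoprolol is increased to 7.5 mg QD". Section 3.6.3 is permissive for both: "the investigator may increase moxonidine and bisoprolol doses to 0.6 mg and 7.5 mg QD, respectively". Section 5.1 differs by arm: for moxonidine, "the investigator may increase moxonidine dose to 0.6 mg QD"; for bisoprolol, "the investigator will increase bisoprolol dose to 7.5 mg QD".

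**The dose continued from week 4.** Section 3.6.3 has "Patients will continue to take moxonidine 0.6 mg/bisoprolol 5 mg until visit V2", the raised dose in one arm and the starting dose in the other. Section 5.1 is symmetric: for bisoprolol, "Patients will continue to take bisoprolol 5 mg (7.5 mg) until next visit V2", and for moxonidine 0.4 mg or 0.6 mg in the same form.

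**The concern.** An investigator cannot follow all of these instructions. A patient still off target on the raised dose at week 4 receives perindopril that day under 3.6.3 and 5.1, and waits until V2 under 3.1 and 3.8. If the investigator waits, the V2 text in 5.1 contains no perindopril step and continues the regimen unless BP is 180/120 mmHg or more. The two schedules are each repeated in several places, so a single typing error does not explain them.

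What is at stake is the interpretation of a secondary endpoint. Section 6.2 compares the proportion at <140/90 mmHg between groups, V2 included. Depending on the schedule followed, that proportion describes either the first-line drug alone or a mixture of monotherapy and combination therapy. The trial is open-label, so whoever chooses between the rules knows the patient's arm. The unequal verbs in 5.1 add a second, smaller opening for early dosing to differ by arm for reasons other than the drug.

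**Working it through.** The plan has no figure to reproduce: section 10.5 states that no formal sample size calculation was made, and the point does not depend on power. The check is a comparison of texts plus some day counting.

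**1. Instructions side by side**

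| Decision | Synopsis and 3.1 | 3.6.3 | 5.1 | 3.8 |
|---|---|---|---|---|
| Week-2 increase | directive, both arms | optional, both arms | optional for moxonidine, directive for bisoprolol | no verb that settles it |
| Dose continued from week 4 | not stated | 0.6 mg / 5 mg | 0.4 (0.6) mg / 5 (7.5) mg | not stated |
| Perindopril added | week 8 | week 4 | week 4 | week 8 / V2 |

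At V2 and V3, 3.6.4 and 3.6.5 act when target is missed; 5.1 continues at any BP <180/120 mmHg.

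**2. Perindopril exposure before V2.** Inputs: the week-4 call is day 28 (4 × 7); V2 is day 56 ± 5 (3.6.2); V4 is day 336 (3.6.5).

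- Added at week 4: 56 − 28 = 28 days before V2. Across the visit window: 51 − 28 = 23 to 61 − 28 = 33 days.
- Added at V2: 56 − 56 = 0 days.
- By V4: (336 − 28)/7 = 44 weeks against (336 − 56)/7 = 40 weeks.

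**3. Consequence for the week-8 proportion.** In one arm, let *p* be the share off target on the raised dose at week 4, and *r* the increase in their probability of reaching target at V2 that comes from adding perindopril at week 4. Moving from the V2 rule to the week-4 rule changes that arm's week-8 proportion by *p* × *r*. The between-group difference changes by *p*ₘ*r*ₘ − *p*ᵦ*r*ᵦ (m = moxonidine, b = bisoprolol). The documents give none of these four quantities, so neither size nor sign can be calculated.

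**4. The arm-specific wording.**

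- The planned step is equal in relative terms: 0.6/0.4 = 1.5 and 7.5/5 = 1.5.
- Section 3.6.2 dispenses moxonidine 0.2 mg at V1 for 42 days in case of titration. Day 56 − day 14 = 42 days, exactly the period from the week-2 call to V2. The moxonidine step therefore does not look meant to be less routine than the bisoprolol one.
- The sentence after the uneven TV2 doses in 3.6.3 uses 0.6 mg and 7.5 mg, and 5.1 is symmetric. The 5 mg is very probably a slip.
- Read literally, the two asymmetries point in opposite directions: TV2 in 3.6.3 favours a higher moxonidine dose, while the verbs in 5.1 favour more escalation of bisoprolol.

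**The case against.** The strongest case against giving this weight is as follows. The trial is labelled explorative, week 8 is one time point of one of seven secondary endpoints, and 10.3 promises descriptive presentation. The BP items in 3.10 and 10.3 mention no between-group comparison; only 6.2 does. The regimen is titrate-to-target with a planned add-on, so by V3 and V4 the proportion describes a treatment strategy under either rule. For V2 and V3, 3.6.4 and 3.6.5 refer the investigator back to the study design, which leads to 3.1. All of this stands and keeps the point minor. It does not remove the conflict: the pointer to the study design covers V2 and V3 but not the telephone calls, and the V2 and V3 text in 5.1 still says otherwise.

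Three stronger readings are tempting, and the documents do not support them.

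- *The protocol doses the arms unequally.* The difference in verbs is confined to 5.1 and may be a translation slip; the synopsis and 3.1 are directive for both drugs and 3.6.3 is optional for both. The uneven TV2 doses are corrected by their own context. The two-week interval given only for bisoprolol (synopsis and 3.8.2) has no consequence, since bisoprolol has a single step and 3.1 sets the same week-2 assessment for both drugs.
- *There is no threshold for acting.* Sections 3.6.3 and 5.1 name none for the calls, but 3.1 and 10.3 give 140/90 mmHg, and 3.6.2 issues a daily BP diary. What is missing is an explicit link from the calls to that target and that diary.
- *The C-telopeptide comparison is biased.* Nothing in the documents allows this to be shown, and the perindopril conflict is the same in both arms.

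**Conclusion.** Minor, but wrong as written. The textual conflict over perindopril timing is certain, as is the disagreement between 3.6.4/3.6.5 and 5.1 at V2 and V3. Its measurable size is nominally 28 days against 0 days of add-on treatment before V2 for a patient off target on the raised dose at week 4. This assumes that the calls and V2 fall on their nominal days and that each rule is applied as written. The consequence is that the week-8 responder proportion is undefined as to treatment: first-line drug alone, or a mix.

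The difference between *may* and *will* in 5.1 is a secondary point. In an open-label trial it is an avoidable route to unequal early dosing, but only a possibility. A reader might infer a bias towards one drug, or an effect on C-telopeptide or other V4 outcomes; neither is claimed, because the share of patients off target at the calls is not given and the arm-specific wordings do not even agree in direction.

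**What to change.** Make one amendment that does the following.

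1. **One perindopril time for both arms in every section.** The default is V2 (week 8), where clinic BP is measured and study drug is dispensed; the documents do not say how perindopril would reach a patient after a telephone call. Change 3.6.3 and 5.1 to match, and align the losartan text in the synopsis and 3.8.4. If the clinical team prefers week 4, change the synopsis (Study Design, Investigated product, Comparative product) and sections 3.1, 3.8.1, 3.8.2 and 3.8.3.1 instead.
2. **One rule at V2 and at V3.** Align 5.1 with 3.6.4 and 3.6.5, so that action follows when BP is not <140/90 mmHg. Withdrawal at 180/120 mmHg or more can stay as a separate rule.
3. **One week-2 rule for both drugs.** In 3.6.3 and 5.1, write that the investigator will, subject to tolerability, increase the dose if BP is not <140/90 mmHg (the target in 3.1), read from the self-monitoring diary.
4. **Correct the TV2 sentence in 3.6.3** to moxonidine 0.4 mg (0.6 mg) / bisoprolol 5 mg (7.5 mg).

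The clinical team should confirm doses and timing. The cost is one amendment with ethics committee approval (12.1 and 13.1); no visit, sample or test is added. The V2 default has a clinical price: patients off target at week 4 receive the add-on 4 weeks later than 3.6.3 and 5.1 now allow.
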